6.2.2 Enrollment, Baseline, and/or Randomization

Enrollment

Participants will become enrolled upon randomization, after meeting all screening criteria and completing all of the baseline assessment procedures.

Baseline Assessments

Those who complete the consent visit and whose screening labs are within range will complete the following baseline assessments from home/online: Qualtrics questionnaire (to assess baseline eating behavior, mood, stress, etc), 24-hour diet recall, and baseline blood draw at LabCorp convenient to them. Those whose screening Craving EMA was completed more than 4 weeks before the class start date will repeat this assessment in order to get baseline data more proximal to when the intervention starts.

Blood draws and lab tests will be done at LabCorp.

Test	Rationale	Screening	Baseline	Follow-up (3 & 6 mos)
HbA1c	Overall glucose control	x	x	x
C-peptide (for those on insulin)	Confirms T2DM in those on insulin	x		
TSH	Rule out untreated thyroid disorder	x		
Comprehensive Metabolic Panel	Rule out liver and kidney dysfunction	x		
Glucose, Plasma (fasting)*	Used to calculate HOMA-IR		x	x
Insulin*			x	x
hsCRP	Examine effects of the diet on		x	x
Lipid Panel	cardiometabolic and inflammatory		x	x
NMR LipoProfile® (Without Graph)—includes lipids	markers		x	x

24-hour dietary recall: Despite limitations of self-report measures in assessing dietary intake, they remain an important tool to assess dietary adherence. 24-hour diet recall provides a measure that complements the ketone measure by providing overall diet composition information that cannot be obtained from ketone measures. We will use the University of Minnesota's Nutrition Data System for Research (NDSR) software to perform 24-hour diet recall (<http://www.ncc.umn.edu/products/>). This is a widely-used dietary analysis program that enables the collection of multiple 24-hour diet recalls and encompasses multiple foods appropriate for diets of type 2 diabetic patients. Dietary recalls will be administered by trained dietetics volunteers by co-investigator [name], a nutrition epidemiologist with extensive history of conducting 24-hour recalls. Recalls will be entered into the NDSR software immediately after completion. Dietary recalls will be conducted without prior notification to avoid changes in diet on the reporting day.

Craving EMA: We hypothesize that a key behavior mechanism by which training in mindfulness can

improve diet adherence is through reducing eating behavior in response to food cravings. This mobile, real-time EMA approach allows us to capture eating-related behavior and that is often brief and automatic and therefore poorly suited to traditional retrospective questionnaires. Participants will complete EMA of food cravings and craving-related eating via smartphones prior to, during, and following the intervention, a total of up to 6 times. During each of these craving-assessment periods, participants will receive mobile cravings assessment via text 3 times per day for 3 days. The text message will ask them to complete a short questionnaire regarding whether they have experienced any food-related cravings in the past few hours, whether they have eaten in response to these cravings, and what they ate. They will also be asked to rate their stress level during the day.

Computerized Cognitive Measures: The computer session will comprise approximately 20-30 minutes of the tasks described below. These tasks can be adjusted to be shorter than their stated length by reducing the number of trials administered. This is a common practice in neuropsychological science research. We will create a 20-30 minute battery from the following tasks:

- Delayed Discounting³⁷; The DD (1 minute) assesses the extent to which individuals value delayed versus proximal rewards. Individuals who discount delayed rewards at a high rate are more likely to engage in substance abuse, overeating, or problem gambling. This 5-trial adaptation of the original Delayed Discounting,³⁸ task has been validated and is an effective way to assess discount rates while reducing participant burden. The primary outcome is the participant's point of indifference, which is computed with intertemporal choice tasks that present a series of discrete choices between a larger quantity of a reward that is delayed and a smaller amount of that commodity that is available immediately.
- Go/No-Go.³⁹ The Go/No-Go task (~12 minutes) is a computer task that measures sustained attention and response control, also termed behavioral inhibition. Participants are asked to watch a rectangle (oriented either vertically or horizontally), and press the spacebar as quickly as possible when the rectangle's color becomes green. In contrast, when the rectangle becomes blue, participants are asked to restrain from pressing the spacebar. The primary outcome is the number of trials correctly identified, and response time, where faster performance and better capacity to inhibit responses to blue rectangles relative to green, indicates better response inhibition.
- Food Stroop.⁴⁰ The food Stroop task (~5 minutes) is an adaptation of the classic Stroop task, and thus provides an easily quantifiable measure of food preoccupation. Subjects are asked to color-name food- and weight-related words written in different-colored inks, compared with neutral words.
- Relative Reinforcing Efficacy (RRE) of Food.⁴¹ This task (~3 minutes) measures the relative reinforcement value of tasty foods as participants indicate how much they would be willing to pay. These choices reflect decisions that people face in the real world when experiencing the motivation to eat.
- Dot Probe.⁴² This modified visual probe task (~4 minutes) measures selective attentional processing of images of food relative to neutral images. The task consists of 10 practice trials and 4 blocks that each consisted of 100 experimental trials, of which 60 are target trials (food–neutral picture pairs) and 40 are filler trials (neutral–neutral picture pairs).

Online questionnaires/self-report measures: We will use a targeted battery of questionnaires assessing food cravings and other eating-related behaviors, as well as standard measures of psychological distress. These will be completed via Qualtrics, and can be completed at home, via the internet. Participants who prefer to come to the lab to complete these using a study computer may schedule a time to do with study staff during business hours.

- Perceived Stress Scale (PSS).⁴³ 10-item measure assessing the degree to which someone perceives stress.
- Patient Health Questionnaire (PHQ-8).⁴⁴ A standardized, well-validated 8-item measure of depressive symptoms.
- Reward-Based Eating Drive (RED).⁴⁵ The 9-item RED scale assesses three aspects of drive to eat (loss of control, lack of satiety, and preoccupation with food). Items are answered on a Likert scale from 1 (not at all like me) to 5 (very much like me). The title of the RED questionnaire provided to participants is “Eating Experiences.” Example items include “I feel out of control in the presence of delicious food” and “When I start eating, I just can’t seem to stop.”³
- Food Craving Questionnaire - Trait Reduced Version (FCQ-T-R).⁴⁶ The 15-item FCQ-T-R assesses (1) preoccupation with food (i.e., obsessive thought about food and eating), (2) loss of control (i.e., difficulty regulating eating behavior when exposed to food cues), (3) positive outcome expectancy (i.e., believing eating to be positively reinforcing), and (4) emotional craving (i.e., tending to crave food when experiencing negative emotion).²
- Stress-related Eating.⁴⁷ The 2 items used in the Midlife in the United States (MIDUS) study asked participants to indicate how they usually experience a stressful event using the following two items: “I eat more of my favorite foods to make myself feel better” and “I eat more than I usually do”. Items are answered on a scale from 1 (a lot) to 4 (not at all). Responses are reverse-coded and summed, with higher scores indicating greater use of food in response to stress. Item correlations are good ($= .80$, $= .81$).⁴
- Palatable Eating Motives Scale.⁴⁸ The 19-item PEMS assesses four motives for eating tasty food (Social, Conformity, Enhancement, and Coping motives) and is modeled after the Drinking Motives Questionnaire (M. L. Cooper, 1994). Items are answered on a 5-point scale with the following options: Almost Never/Never; Some of the Time; Half of the Time; Most of the Time; Almost Always/Always.¹
- 1-item Stress Eating.¹⁸ This 1-item measure has been shown to predict weight gain and worsened metabolic factors in times of stress. This item asks, “how much do you tend to eat when you are under moderate stress?” and is responded to on a 5-point scale from much less than usual to much more than usual.⁵
- Weight Efficacy Lifestyle Questionnaire – Short Form (WEL-SF).⁴⁹ The ability to adhere to a diet in the face of difficult situations, such as dietary lapses, socializing, and peer pressure is integral to long-term maintenance of intervention effect. We will assess dietary adherence self-efficacy using the 8-item which assesses abilities to adhere to dietary prescriptions in a variety of situations.
- Loss of control over Eating – Brief (LOCES-Brief).⁵⁰ This 7-item measure assess perceived control over one’s eating. Items are assessed on a 100mm visual analogue scale ranging from “not at all hungry” or “not at all anxious” etc., to “extremely hungry” or “extremely anxious” etc.
- Food Acceptance and Action Questionnaire (FAAQ).⁵¹ This 10-item questionnaire applies constructs of acceptance and mindfulness to eating behavior. Higher scores indicate greater acceptance of motivations to eat. Items are answered on a 6-point Likert scale ranging from 1 (very seldom true) to 6 (always true). A summary score is calculated by summing the scores from all items – higher scores indicate greater acceptance of motivations to eat.⁹
- Control of Eating Questionnaire (CoEQ).⁵² This 21-item measure assesses food craving for sweet and savory, dietary restraint, and mood over the previous 7 days. Items are assessed on a 100mm visual analogue scale that varies in its anchors to capture the experience of food craving assessed by a given item.⁷

- Dutch Restrained Eating Scale.⁵³ This 10-item subscale of the Dutch Eating Behavior Questionnaire assesses the frequency of restrained eating behavior. Items are assessed on a 5-point likert scale ranging from 1 (never) to 5 (very often).⁸
- Five Factor Mindfulness Questionnaire (FFMQ).⁵⁴ We will use the short-form of the FFMQ which assesses general tendencies to be mindful in experiences of daily life.
- Promis-29 (www.nihpromis.org): A collection of 4-item short forms assessing anxiety, depression, fatigue, pain interference, physical function, sleep disturbance, and ability to participate in social roles and activities as well as a single pain intensity item. The PROMIS measures a system of highly reliable, precise measures of patient-reported health status for physical, mental, and social well-being.
- Self-Compassion Scale Short Form (SCS-SF13).⁵⁵ The SCS-SF is a 12-item measure that assesses dimensions of self-compassion including self-kindness, self-judgment, common humanity, isolation, mindfulness, and over-identification.

Weight

- One of the goals of dietary adherence for persons with T2DM is weight loss. We will use the same scale to weigh participants at each time point.

Randomization

Participants will be randomized to intervention groups after completion of all screening and baseline assessment steps, and before initiation of intervention. Randomization will be done approximately 2 weeks prior to the start of classes in order to minimize post-randomization drop-out due to life circumstances that might affect participant ability to attend classes (e.g. such as job loss/change, family emergency, etc).

6.2.3 Blinding

Not applicable for this study.

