Carbohydrate restricted (CR) diets can provide an important biomarker (ketone level) for dietary adherence and may improve glucose control in T2DM. Current recommendations from the ADA suggest that a variety of carbohydrate levels may be appropriate for persons with T2DM, including reduced carbohydrate diets.²⁴ We aim to restrict carbohydrates to approximately 10% of caloric intake, or about 50 g/day in this study for several reasons. This induces a low level of ketone production, which has been termed “nutritional ketosis.” This provides an *important biomarker* for dietary adherence that we aim to utilize in this study (See Measures in the Approach section). Unlike diabetic ketoacidosis, nutritional ketosis is a stable metabolic state associated with potential health benefits in persons with T2DM. Several studies suggest that lowering carbohydrate intake to this range can improve glucose control, insulin resistance, plasma triglycerides, plasma C-reactive protein, and body weight.²⁵⁻³¹ For example, in a short-term study conducted in a metabolic ward, 10 overweight persons with T2DM consumed their usual diets for 7 days, followed by a CR diet (21 g/day carbohydrate) for 2 weeks. Participants’ mean 24-hour plasma profiles of glucose levels normalized, mean HbA1c decreased from 7.3% to 6.8%, and insulin sensitivity improved by approximately 75% on the carbohydrate restricted diet.³² Our group has compared a CR diet (< 50 grams/day carbohydrate) to a conventional calorie-restricted diet for T2DM and found a significantly greater improvement in mean HbA1c in those on the carbohydrate restricted diet group (see Preliminary data in Approach for further details).³¹

As in other diet interventions, adherence remains a key challenge. In our diabetes pilot study, we found that with limited long-term behavioral support, by 12-months the improvements in HbA1c had declined -0.2% (-0.8 to 0.4, p = .5; unpublished data). While we considered including different diets in the current study, our primary focus is on the role of mindfulness-based intervention components on dietary adherence. We thus choose to keep the diet consistent across groups, and believe a low carbohydrate diet is a good choice because it offers an effective biomarker of adherence, potential health benefits for persons with T2DM, and clear adherence challenges.

This study includes several key innovations.

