25, i.e. normal vs. overweight/obese). Neither participants nor study personnel will be blinded to treatment arm.

Primary mechanistic outcome(s): Our primary hypothesized mechanism is reduction in **frequency of eating in response to cravings** as a result of enhanced ability to address food cravings with mindfulness training. Our key measure of this mechanism is frequency of eating in response to cravings using ecological momentary assessment (EMA).

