For each of these measures, our primary analysis will be comparison of changes from baseline to follow-up time points between groups (see overall analysis approach above). We will also assess changes from baseline to follow-up within each group to help assess the potential effect of each intervention arm on these measures. We will also test for preliminary evidence that each of these proposed mechanisms is associated with dietary adherence. Dietary adherence will be measured two ways: (1) proportion of blood ketone measures $\geq 0.3\text{mmol/L}$; (2) proportion of kcal from carbohydrate, using 24-hour diet recall. Each of our mechanism measures are continuous variables. We will therefore assess correlations between each of the mechanism measures and the dietary adherence measures, using linear regression. Finally, we will perform initial analysis of whether there are differences in two important clinical outcomes between intervention groups: HbA1c (to examine glycemic control) and weight. These clinical outcomes should result from our intermediate behavioral outcome of improved dietary adherence. We do not expect to have adequate sample-size in either phase of this study to address this question, but believe that preliminary assessment of these outcomes should be performed in case there are dramatic differences between groups even with limited sample size.

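### The 24-hour recall interviewers are left unblinded at follow-up, although no task described for them requires knowing the arm

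*Combined protocol and SAP*

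**What the plan says.** Section 6.2.3 consists of one line: "Not applicable for this study". Section 3 is explicit: "Neither participants nor study personnel will be blinded to treatment arm". The two agree. Neither gives a reason or makes an exception for anyone who collects outcomes.

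On the recall, Section 6.2.2 says "Dietary recalls will be administered by trained dietetics volunteers", with entry into the nutrition software straight afterwards. It accepts the weakness of the method ("Despite limitations of self-report measures in assessing dietary intake, they remain an important tool to assess dietary adherence") and states one safeguard: "Dietary recalls will be conducted without prior notification to avoid changes in diet on the reporting day".

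Section 9.6 says "Dietary adherence will be measured two ways": the proportion of blood ketone readings at or above 0.3 mmol/L, and "proportion of kcal from carbohydrate, using 24-hour diet recall". It does not rank the two. The Précis makes better adherence in Ed+MBI than in Ed the hypothesis of R33 Aim 2; Section 9.5.2 lists adherence among the secondary clinical outcomes. On the diet itself, Section 2.2 says "We thus choose to keep the diet consistent across groups".

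**The concern.** Participants and class instructors cannot be blinded to a mindfulness course. It does not follow that blinding has no application in the trial. A 24-hour recall is an interview: how far the interviewer probes for snacks, drinks and portion sizes affects what is recorded. An interviewer who knows the arm and expects the mindfulness group to do better could probe that group less, or differently, without intending to.

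Unannounced recalls stop participants from changing what they eat on the reporting day. They do nothing about interviewer expectation. What is at stake is the credibility of one of two unranked measures behind R33 Aim 2. If the recall favoured Ed+MBI and the ketone readings did not, the plan as written would leave the investigators unable to answer the obvious question about how the recall was collected.

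**Working it through.** The plan states no figure on this point, so there is none to reproduce. The check is a reading of the text followed by two illustrations.

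**1. Could the bias cancel?** Section 6.2.2 places the baseline recall before randomization, so no baseline interviewer can know the arm. Follow-up recalls (3 and 6 months in Section 6.2.4; also 12 months under the R33 schedule in Section 3) come after assignment. Section 9.6 names the between-group comparison of change from baseline as its primary analysis. I assume that R33 Aim 2 is tested in the same way, since no separate method is given. If follow-up error has mean e1 in one arm and e0 in the other, and baseline error has the same mean in both, the estimated difference in change is shifted by e1 − e0. Subtracting baseline does not remove it.

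**2. Is masking feasible on the plan's own description?**
- The interviewers are volunteers. No teaching or randomization role is described for them.
- Both arms follow the same diet, so the foods reported should not in themselves reveal the arm.
- Baseline recalls are among the assessments done from home or online, not in class (Section 6.2.2).
- Recalls go into the nutrition software, whereas assignments are held in the Salesforce database (Sections 4.3 and 9.2).
- Data forms already carry coded IDs (Sections 10.1 and 11.3).

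**3. What could one missed item do?** The 15 g item is an assumption. At 4 kcal/g it is 60 kcal. Two energy levels follow from the plan:
- Sections 2.2 and 5.2, 50 g as about 10% of energy: 50 × 4 / 0.10 = 2000 kcal.
- Section 5.2, protein: 80 × 4 / 0.20 = 1600 kcal and 100 × 4 / 0.25 = 1600 kcal.

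An unreported item leaves both the numerator and the denominator, so dividing 60 by total energy is not exact.

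| Energy | Case | True share | Recorded share | Shift (points) |
|---|---|---|---|---|
| 2000 kcal | true share 10% | 200/2000 = 10.0% | 140/1940 = 7.2% | 2.8 |
| 2000 kcal | recorded share 10% | 260/2060 = 12.6% | 200/2000 = 10.0% | 2.6 |
| 1600 kcal | true share 10% | 160/1600 = 10.0% | 100/1540 = 6.5% | 3.5 |
| 1600 kcal | recorded share 10% | 220/1660 = 13.3% | 160/1600 = 10.0% | 3.3 |

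The shift in an arm mean is this value times the excess fraction of that arm's recalls affected, which is unknown. At an assumed one third it is 2.6/3 = 0.9 to 3.5/3 = 1.2 points; at one tenth it is 0.3 to 0.4 points.

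**4. What would a given bias do to a test?** Let b be an interviewer-induced shift in SD units, with no true effect and a two-sided t-test at 0.05. The noncentrality is b / √(1/n1 + 1/n2), with n1 + n2 − 2 degrees of freedom. For b = 0.2 this is 0.2/0.258 = 0.77 with 30 vs 30, and 0.2/0.194 = 1.03 with 40 vs 80.

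| b (assumed) | False-positive rate, 30 vs 30 (R61) | False-positive rate, 40 vs 80 (R33) |
|---|---|---|
| 0 | 5.0% | 5.0% |
| 0.1 | 6.7% | 8.1% |
| 0.2 | 11.9% | 17.6% |
| 0.3 | 20.8% | 33.6% |

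The documents give no SD for the recall measure, so the points in step 3 cannot be converted to values of b.

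**The case against.** The study is openly declared open-label and its two statements agree, so nothing is hidden or contradictory. That stands: this is a design choice that can be improved, not an error.

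The reach is narrow, and that stands too. The primary outcome is smartphone EMA, the other adherence measure is a blood ketone reading with meter downloads as a check, and adherence is listed as secondary. Only follow-up recalls are exposed. Unblinded participants can mention their classes, and their own reporting bias remains whatever the interviewer knows.

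It is also fair to say that the volunteers' lack of any need to know the arm is inferred from what the documents describe; their other duties and access are not set out. The documents do not say that they will be told the arm, only that nobody is blinded.

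Finally, other staff contacts are open as well: weighing and cognitive testing (Section 6.2.4), and clarification of questionable EMA responses with participants (Section 10.3.3). The change proposed here does not address those. That limits what it achieves, but is no reason to leave the recall interviewers unmasked.

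**Conclusion.** The point holds as a cheap improvement. The plan leaves recall interviewers unblinded without a reason, on a measure that enters R33 Aim 2, where masking appears practicable on the plan's own description. Arm-dependent probing at follow-up could bias the comparison of change, in a direction and amount that cannot be determined from the documents. The 2.6 to 3.5 points per missed item and the false-positive rates rest on an assumed item, an assumed frequency and assumed values of b; they show that a modest bias could matter, not that one exists.

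Three stronger readings are tempting and are not supported:
- A reader might infer that interviewer expectation does bias the recall. The documents contain no evidence of differential probing.
- A reader might infer that masking would cost nothing. The documents do not discuss its cost or practicality, and it needs some procedure.
- A reader might infer that the primary outcome or the whole adherence comparison is compromised. The EMA outcome and the ketone measure do not pass through these interviewers.

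**What to change.** Amend Section 6.2.3 and the blinding sentence in Section 3 together; changing only one would create a contradiction that does not now exist. Suggested content for both:

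- Participants and class instructors are not blinded.
- Interviewers for the 24-hour recall are not told the arm and have no access to assignments in the study database.
- They work from call lists that carry the ID only, with no arm or class information.
- At the start of each call they ask the participant not to mention their classes.
- After each recall they record whether the arm became known.

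If masking is judged impracticable, say why in place of the present one-line statement. Report the proportion of follow-up recalls with known arm, by arm, alongside the adherence results.

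The cost is a database access restriction, call-list handling, a line in the script and one recorded item per recall; no extra staff appear to be needed. The downside is that masking will be incomplete. Participants' own reporting bias, the EMA primary outcome and the ketone measure are unchanged.
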